### **ASAS20 at week 16**

Response at Week 16 to ASAS20 for Secukinumab (early-tapering) versus placebo will be evaluated using a logistic regression model with treatment as a factor and baseline weight as a covariate.

Refer to Appendix section 5.1 for calculation of ASAS20.

### **ASAS-NSAID at Week 12**

Between-treatment differences in the change in ASAS-NSAID relative to baseline will be evaluated using a mixed-effect model repeated measures (MMRM). Treatment group and analysis visit as factors, baseline ASAS-NSAID and weight as continuous covariates. Treatment by analysis visit and baseline ASAS-NSAID by analysis visit will be included as interaction terms in the model. Initially an unstructured covariance structure will be assumed for the model. The significance of the Secukinumab pooled treatment effect will be determined from a linear contrast comparing the (mean of the) two Secukinumab regimens to placebo. The significance of the two individual Secukinumab treatment group effects will be determined from the pairwise comparisons performed between Secukinumab regimens and placebo.

Refer to Appendix section 5.1 for calculation of ASAS-NSAID scores.

### **BASDAI at Week 12/16**

The change from baseline to Week 12/16 in total BASDAI will be analyzed using a MMRM with treatment regimen and analysis visit as factors and weight and baseline score as continuous covariates. Treatment by analysis visit and baseline by analysis visit will be included as interaction terms in the model. An unstructured covariance structure will be assumed for this model. The significance of the Secukinumab treatment effect will be determined from the pairwise comparisons performed between Secukinumab regimens and placebo. The adjusted (LS) mean difference will be calculated as a point estimate together with the corresponding 95% confidence interval and p-value.

Refer to Appendix section 5.1 for calculation of BASDAI scores.

### **Other secondary variables**

## **SF-36 PCS**

For the change in SF-36 PCS, between-treatment differences will be evaluated using a mixed effect repeated measures model (MMRM). Treatment group and analysis visit will be included as categorical factors and baseline SF-36 PCS score and weight as continuous covariates. Treatment by analysis visit and baseline SF-36 PCS score by analysis visit will be included as interaction terms in the model. An unstructured covariance structure will be assumed for the model. The significance of the Secukinumab treatment effect will be determined from the pairwise comparisons performed between Secukinumab regimens and placebo.

### **2.7.3 Handling of missing values/censoring/discontinuations**

Missing data for ASAS20 response and other binary efficacy variables (e.g. ASAS5/6, etc.) for data up to Week 20 will be handled as follows:

1. Subjects who drop out of the trial for any reason will be considered non-responders from the time they drop out through Week 20.
2. Subjects who do not have the required data to compute response (e.g. ASAS components) at baseline and at the specific time point will be classified as non-responders.

Patients who were unblinded prior to the scheduled timepoint will be considered non-responders from the time of unblinding up to Week 16. The secondary analysis will use the non-responder imputation only.

## **2.8 Safety analyses**

For all safety analyses, the Safety set will be used.

Summaries may be performed separately for different treatment periods.

The analyses of the follow-up period will be limited to summaries for treatment-emergent adverse events, and serious adverse events.

Safety analyses will be performed on treatment received or actual treatment as described below:

The actual treatment or treatment received for summaries of safety data will differ to the treatment assigned at randomization only if a subject received the wrong treatment during the entire study.

For those patients who received not the treatment randomized, i.e. who received erroneously the wrong treatment at least once, an additional AE listing will be prepared displaying which events occurred after the treatment errors and also the relationship with study drug.

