The occurrence of relevant protocol deviations will be determined. After these actions have been completed and the database has been declared to be complete and accurate, it will be locked and the treatment codes will be unblinded and made available for data analysis. Any changes to the database after that time can only be made after written agreement by Trial Statistician and Statistical Reporting and the Clinical Trial Leader.

8.4 **Data Monitoring Committee**

Not required.

8.5 **Adjudication Committee**

Not required.

9 Data analysis

Summary statistics for continuous variables will generally include the number of subjects (N), minimum, lower quartile, mean, median, upper quartile, and maximum. For categorical or binary variables, the number and percent of subjects in each category will be presented. P-values presented will be two-sided unless otherwise specified.

Inferential efficacy comparisons with placebo will generally focus on the first 12-weeks of treatment.

Data analyses will be presented by treatment regimen. Efficacy and safety data for the placebocontrolled period (or the entire treatment period as appropriate) will be presented by the following 3 treatment groups. These treatment groups represent the regimens subjects will be eligible to be randomized to.

Secukinumab ("delayed tapering") regimen: Secukinumab 150 mg s.c. at Week 0, 1, 2, 3, 4, 8, 12, 16 and 20; Placebo injections at Week 5, 6 and 7 and 17, 18. 19.

Secukinumab ("early tapering") regimen: Placebo at Weeks 0, 1, 2, 3 followed by Secukinumab 150 mg s.c. at Week 4, 5, 6, 7, 8, 12, 16 and 20 with additional Placebo injections at week 17, 18. 19.

Placebo regimen: Placebo at Weeks 0, 1, 2, 3, 4, 5, 6, 7, 8 and 12. From Week 16, patients will be switched to receive Secukinumab 150 mg s.c. at Week 16, 17, 18, 19, and 20.

9.1 **Analysis sets**

Randomized set: The randomized set will be defined as all subjects who were randomized.

Full analysis set (FAS): The FAS will be comprised of all subjects from the randomized set to whom study treatment has been assigned. Following the intent-to-treat principle, subjects will be evaluated according to the treatment assigned to at randomization, and in the actual stratum if stratified randomization is used.

Safety set: The safety set includes all subjects who took at least one dose of study treatment during the treatment period. Subjects will be evaluated according to treatment received.

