#### Treatment arms

Patients will be randomized 1:1:1 to one of the following treatment groups:

- **Secukinumab - delayed NSAID tapering:** Secukinumab 150 mg s.c. at weeks 0, 1, 2, 3, 4, 8, 12, 16 and 20 with placebo injections at Week 5, 6, 7 and 17, 18, 19 to maintain the blind.
- **Secukinumab – early NSAID tapering:** Placebo at weeks 0, 1, 2, 3 to maintain the blind; followed by Secukinumab 150 mg s.c. at Week 4, 5, 6, 7, 8, 12, 16 and 20 with intermittent Placebo injections at week 17, 18, 19 to maintain the blind.
- **Placebo:** Placebo at weeks 0, 1, 2, 3, 4, 5, 6, 7, 8 and 12. After the Week 16 assessments of the secondary endpoint have been performed, these patients will receive Secukinumab 150 mg s.c. at weeks 16, 17, 18, 19 and 20.

The patients will be stratified at randomization according to their status of prior TNF $\alpha$  inhibitor exposure, i.e. TNF $\alpha$  inhibitor naïve patients or TNF $\alpha$  inhibitor inadequate responders (TNF $\alpha$ -IR). The only condition that will be placed on enrollment targets for each stratum is that no less than 60% (i.e. 114) of patients are TNF $\alpha$  inhibitor naïve, i.e., no more than 40% (i.e. 76) of patients are TNF $\alpha$ -IR. In theory the percentage of TNF $\alpha$  inhibitor naïve patients could reach 100%, although that is not anticipated.

For primary analysis both the secukinumab treatment arms will be pooled and compared against placebo.

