### **2.8.1 Adverse events (AEs)**

The crude incidence of treatment emergent adverse events (i.e. events started after the first dose of study treatment or events present prior to the first dose of study treatment but increased in severity based on preferred term, and events until 30 days for AE and SAE after last dose of study treatment) will be summarized by primary system organ class and preferred term.

The summaries will be presented separately by study periods i.e. week 1-16 and after week 16.

In addition, exposure time-adjusted incidence rates including 95% confidence intervals will be provided for the entire treatment period to adjust for differences in exposure. A graphical display of the crude rates and exposure-adjusted incidence rates will be presented for all AEs and serious AEs by system organ class. A graphical display of relative frequencies within system organ classes and relative risks, as appropriate, will be presented.

Adverse events will be summarized by presenting, for each treatment group, the number and percentage of patients having at least one AE, having an AE in each primary system organ class and having each individual AE (preferred term).

The most common adverse events reported (>1 % in any group for each preferred term in the SOC-PT table or > 1 % in any group) will be presented in descending frequency according to its incidence in total secukinumab group (combining all secukinumab treatment groups) starting from the most common event.

Summaries (crude incidences only) will also be presented for AEs by severity and for study treatment related AEs. If a particular AE 'severity' is missing, this variable will be listed as missing and treated as missing in summaries. If a subject reported more than one adverse event with the same preferred term, the adverse event with the greatest severity will be presented. If a subject reported more than one adverse event within the same primary system organ class, the subject will be counted only once with the greatest severity at the system organ class level, where applicable.

Separate summaries will be provided for

- adverse events suspected to be related to study drug by the investigator
- deaths
- adverse events leading to discontinuation
- adverse events leading to temporary dose interruption.

The MedDRA version used for reporting the study will be described in a footnote.

Follow-up period summaries will be done for all patients in follow-up.

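### Safety treatment is fixed at the randomised arm, so the early arm's placebo lead-in counts as secukinumab and the whole-period exposure-adjusted rates mix placebo and active time in two of three arms

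*SAP*

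**What the plan says.** - **Grouping.** SAP 2.8 states that the treatment used for safety summaries "will differ to the treatment assigned at randomization only if a subject received the wrong treatment during the entire study". Protocol Section 9 (Data analysis) says that efficacy and safety data "will be presented by the following 3 treatment groups", and these are the three randomised regimens.
- **Dosing.** In SAP 1.1 (Treatment arms), allocation is 1:1:1. The early arm receives "Placebo at weeks 0, 1, 2, 3 to maintain the blind; followed by Secukinumab 150 mg s.c. at Week 4". In the placebo arm, once the Week 16 assessments are done, "these patients will receive Secukinumab 150 mg s.c. at weeks 16, 17, 18, 19 and 20".
- **When counting starts.** SAP 2.1.1 includes the placebo syringe in study treatment. Treatment-emergent events (2.8.1) and duration of exposure (2.4.1) both start at the first dose of study treatment, whichever drug that is.
- **Periods.** SAP 2.8.1 and Protocol 9.5.3 show adverse-event summaries separately for Weeks 1-16 and after Week 16. SAP 2.1.1 ends Treatment Period 1 before the Week 16 dose and Treatment Period 2 at Week 20. SAP 2.8, however, describes summaries by period as optional.
- **Exposure-adjusted rates.** SAP 2.8.1 says that these "will be provided for the entire treatment period to adjust for differences in exposure", with no split at Week 4 or Week 16. Section 2.8.1.2 plans crude and exposure-adjusted rates for events of special interest, including infections.
- **Combined group.** Common events are listed most frequent first, "according to its incidence in total secukinumab group (combining all secukinumab treatment groups". The SAP does not define this group further.

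**The concern.** Two arms change drug by design, and the safety grouping follows neither change. An event on Day 10 in the early arm, before any secukinumab, is tabulated in a secukinumab arm. An event in Week 18 in the placebo arm, after the switch, enters that arm's whole-period rate.

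The exposure-adjusted rates are meant to correct for unequal exposure. Dividing by time on study does not do that when the time itself mixes two drugs. The mixing pulls a secukinumab-to-placebo rate ratio towards one, so if secukinumab raises an event rate the excess is understated. This matters most for infections: Protocol 3.6.1.1 reports that they were more frequent on secukinumab than on placebo in an earlier trial in this disease.

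**Working it through.** The documents give no figure for this point, so there is none to reproduce.

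**Inputs from the documents.** Equal arms. Early arm: placebo for 4 weeks, then secukinumab. Delayed arm: secukinumab from Week 0. Placebo arm: placebo for 16 weeks, then secukinumab. Treatment period: 20 weeks.

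**Assumptions.** The event rate is constant at 1 on placebo and RR on secukinumab. Follow-up is complete. RR is not given in the documents, so a range of 1.25 to 3 is shown.

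**Share of time on the other drug**
- Early arm on placebo: 4/16 = 25% to Week 16 and 4/20 = 20% to Week 20. Across both secukinumab arms: 4/32 = 12.5% and 4/40 = 10%.
- Placebo arm on secukinumab: 0/16 to Week 16 and 4/20 = 20% to Week 20.

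**Apparent rates to week T (16 or 20)**
- Early = [4 + (T − 4)·RR]/T
- Delayed = RR
- Placebo arm = [16 + (T − 16)·RR]/T
- Pooled = (early + delayed)/2

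For RR = 1.5 and T = 20: early = (4 + 24)/20 = 1.40; placebo arm = (16 + 6)/20 = 1.10; pooled = (1.40 + 1.50)/2 = 1.45. The ratios to the placebo arm are 1.40/1.10 = 1.27, 1.50/1.10 = 1.36 and 1.45/1.10 = 1.32.

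| True RR | Early, 20 wk | Delayed, 20 wk | Pooled, 20 wk | Early, Wk 1-16 | Delayed, Wk 1-16 | Pooled, Wk 1-16 |
|---|---|---|---|---|---|---|
| 1.25 | 1.14 | 1.19 | 1.17 | 1.19 | 1.25 | 1.22 |
| 1.5 | 1.27 | 1.36 | 1.32 | 1.38 | 1.50 | 1.44 |
| 2.0 | 1.50 | 1.67 | 1.58 | 1.75 | 2.00 | 1.88 |
| 3.0 | 1.86 | 2.14 | 2.00 | 2.50 | 3.00 | 2.75 |

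Assigning events and time to the drug actually being taken returns the true RR in every cell.

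**Illustration with incidences in the protocol.** Study CAIN457F2305 had any-event incidence to Week 16 of 69.6% on the 150 mg regimen and 55.7% on placebo. The constant-hazard ratio is ln(1 − 0.696)/ln(1 − 0.557) = 1.46. Early-arm incidence to Week 16 would be 1 − exp[−(4·λp + 12·λs)] = 66.6%, where λp and λs are the weekly hazards on placebo and secukinumab. The crude difference of 13.9 points would then show as 10.9 for the early arm and 12.4 pooled, and stay 13.9 for the delayed arm. The 20-week rate ratio would fall from 1.46 to 1.25 (early), 1.34 (delayed) and 1.30 (pooled).

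Study CAIN457F2310, whose dose and loading this trial copies (Protocol 9.7), had 65.3% against 63.5%, a hazard ratio of 1.05. There the 20-week ratios would be 1.03 to 1.04. With almost no difference, there is almost nothing to dilute.

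**The case against.** The strongest defence is that the plan already contains a clean comparison. The crude summaries split at Week 16, Period 1 closes before the Week 16 dose, and the delayed arm is on secukinumab from the start. Delayed versus placebo in Weeks 1-16 is therefore planned, randomised and undiluted. Display by regimen is prespecified, safety is an exploratory objective, and no safety test is planned. Protocol 9.3 counts active and placebo injections separately, and SAP 2.4.1 has a treatment-sequence label showing the placebo arm's switch.

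All of this stands, and it rules out several stronger readings that a reader might infer:
- **That every safety comparison is diluted.** Delayed versus placebo in Weeks 1-16 is not.
- **That the placebo arm's secukinumab time enters all the tables.** It enters the whole-period rates, not the Weeks 1-16 tables.
- **That the combined secukinumab group is the planned safety contrast.** The SAP names it only to order a table, so the pooled ratios above are illustrations.
- **That dilution should be computed to Week 24.** The treatment period ends at Week 20, duration of exposure stops there, and follow-up is summarised separately.

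The defence does not reach the remaining gap. No display splits at Week 4. The sequence label for the early arm shows no placebo lead-in, and SAP 2.8 does not adopt the sequence grouping. Counting injections does not move events or person-time.

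**Conclusion.** The point holds in two places. The early arm's Weeks 0-4 count as secukinumab in every adverse-event display, and the whole-period exposure-adjusted rates mix the two drugs in the early and placebo arms.

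For an assumed true rate ratio of 1.5 to 2.0, the 20-week pooled ratio would read 1.32 to 1.58. In Weeks 1-16 only comparisons that include the early arm are affected: 1.38 to 1.75 for early versus placebo and 1.44 to 1.88 pooled.

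These sizes rest on constant rates and complete follow-up. Rates that change over time on study would alter them, and a drug with no effect on an event would show no distortion. The efficacy analyses are untouched. The change is worth making because the affected rate is the one presented as adjusting for exposure.

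**What to change.** In SAP 2.8 and 2.8.1:
1. Compute the whole-period exposure-adjusted rates, and one additional display of adverse events and events of special interest, by treatment at onset. Events and person-time before a patient's first secukinumab injection are placebo; those from that injection onward are secukinumab. State how an onset on the injection date itself is assigned.
2. Ignore later blinding placebo injections. A rule keyed to the most recent injection would mislabel secukinumab-treated time: Weeks 5-8 and 17-20 in the delayed arm (3 + 3 weeks) and Weeks 17-20 in the early arm (3 weeks). That is 9 weeks wrongly assigned, against the 4 lead-in weeks corrected.
3. Define the combined secukinumab group on the same basis, and say whether it includes placebo-arm patients after the Week 16 switch.
4. Make 2.8 agree with 2.8.1 on whether summaries by period are optional or required.
5. Keep the Weeks 1-16 and after-Week-16 tables by randomised regimen as the randomised comparison.

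The cost is one derived variable and extra tables. Injection dates are already recorded (Protocol 6.3). The at-onset comparison is not purely randomised: the placebo time it gains from Weeks 0-4 comes before NSAID tapering, so it should sit beside the randomised tables, not replace them.

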### **2.8.1 Adverse events (AEs)**

The crude incidence of treatment emergent adverse events (i.e. events started after the first dose of study treatment or events present prior to the first dose of study treatment but increased in severity based on preferred term, and events until 30 days for AE and SAE after last dose of study treatment) will be summarized by primary system organ class and preferred term.

The summaries will be presented separately by study periods i.e. week 1-16 and after week 16.

In addition, exposure time-adjusted incidence rates including 95% confidence intervals will be provided for the entire treatment period to adjust for differences in exposure. A graphical display of the crude rates and exposure-adjusted incidence rates will be presented for all AEs and serious AEs by system organ class. A graphical display of relative frequencies within system organ classes and relative risks, as appropriate, will be presented.

Adverse events will be summarized by presenting, for each treatment group, the number and percentage of patients having at least one AE, having an AE in each primary system organ class and having each individual AE (preferred term).

The most common adverse events reported (>1 % in any group for each preferred term in the SOC-PT table or > 1 % in any group) will be presented in descending frequency according to its incidence in total secukinumab group (combining all secukinumab treatment groups) starting from the most common event.

Summaries (crude incidences only) will also be presented for AEs by severity and for study treatment related AEs. If a particular AE 'severity' is missing, this variable will be listed as missing and treated as missing in summaries. If a subject reported more than one adverse event with the same preferred term, the adverse event with the greatest severity will be presented. If a subject reported more than one adverse event within the same primary system organ class, the subject will be counted only once with the greatest severity at the system organ class level, where applicable.

Separate summaries will be provided for

- adverse events suspected to be related to study drug by the investigator
- deaths
- adverse events leading to discontinuation
- adverse events leading to temporary dose interruption.

The MedDRA version used for reporting the study will be described in a footnote.

Follow-up period summaries will be done for all patients in follow-up.

A listing of non-treatment emergent adverse events will be done. These adverse events occurred before the first dose of the study treatment.

Algorithms for date imputations will be provided in Programming Specifications.

If for a same patient, several consecutive AEs (irrespective of study treatment causality, seriousness and severity) occurred with the same SOC and PT:

- a single occurrence will be counted if there is  $\leq 1$  day gap between the end date of the preceding AE and the start date of the consecutive AE
- more than one occurrence will be counted if there is  $> 1$  day gap between the end date of the preceding AE and the start date of the consecutive AE

For occurrence, the presence of at least one SAE / SAE suspected to be related to study treatment / non SAE has to be checked in a block e.g., among AE's in a  $\leq 1$  day gap block, if at least one SAE is occurring, then one occurrence is calculated for that SAE

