5.5.8 Prohibited treatment

Use of the treatments displayed in Table 5-1 is NOT allowed after the start of the washout period unless otherwise specified below.

Live vaccines should not be given until 12 weeks after last study treatment administration.

Table 5-1	Prohibited treatment
i able 5- i	Prombiled freatment

Prohibited treatments	Washout period (before randomization)
Etanercept*	4 weeks
Infliximab*	8 weeks
Adalimumab, golimumab, certolizumab*	10 weeks
Unstable dose of MTX or sulfasalazine (until Week 12)	4 weeks
Other DMARD (except MTX or sulfasalazine)	4 weeks
Leflunomide	8 weeks
Leflunomide with cholestyramine washout	4 weeks
Systemic corticosteroids > 10 mg prednisone equivalent** (until Week 12)	2 weeks
Intra-articular steroids injections (until Week 12)	4 weeks
Any investigational treatment or participation in any interventional trial	4 weeks or 5 half-lives (whichever is longer)
Analgesics other than paracetamol/acetaminophen or low strength opioids PRN	4 weeks
Live vaccinations	6 weeks

^{*}These agents fall under the category of biologic immunomodulators and are prohibited medications. Administration of these agents requires study discontinuation (see Section 5.5.8).

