5.5.14 Early study termination

The study can be terminated at any time for any reason by Novartis for any reason specified in the clinical trial study contract. Should this be necessary, the patient should be seen as soon as possible and treated for a prematurely withdrawn patient. The investigator may be informed of additional procedures to be followed in order to ensure that adequate consideration is given to the protection of the patient's interests. The sponsor will be responsible for informing the Institutional Review Board/Independent Ethics Committee (IRBs/IECs) of the early termination of the trial.

6 Visit schedule and assessments

Table 6-1 lists all of the assessments and indicates with an "x" when the Visits are performed.

For visits scheduled through Week 4, the study treatment should not be administered less than 7 days after the previous administration. For visits scheduled after Week 4, the study treatment should not be administered less than 14 days after the previous administration. At a minimum, patients will be contacted for safety evaluations during the 30 days following the end of treatment visit at Week 20, including a final contact at the 30-day point. Documentation of attempts to contact the patient should be recorded in the source documentation.

Subjects who prematurely discontinue should return for the End-of-treatment visit (corresponds to the week 20 visit) 4 weeks after the last study treatment administration, as well as return for the follow-up (week 24). If they refuse to return for these assessments or are unable to do so, every effort should be made to contact them or a knowledgeable informant by telephone to determine the reason.

Screening will be flexible (up to 10 weeks) in duration based on the time required to washout prior anti-rheumatic and other medications and will have a duration, during which time the patient will sign the informed consent form (ICF), be evaluated for eligibility and sufficient time is allowed for potential medication washout, in addition to all other assessments indicated in Table 6-1.

Screening will consist of 2 consecutive visits. During Screening Visit 1, initial assessments will be performed as outlined in Table 6-1. At that visit, the duration of the washout period will be determined and Screening Visit 2 will be performed as follows:

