7.1 Adverse events

An AE is the appearance or worsening of any undesirable sign, symptom, or medical condition occurring after first intake of study drug even if the event is not considered to be related to study drug. Study drug includes the investigational drugs under evaluation that are given during any period of the study.

Medical conditions/diseases present before first intake of study drug are only considered adverse events if they worsen after study start. Abnormal laboratory values or test results constitute AEs only if they induce clinical signs or symptoms, require dose reduction or temporary or permanent study drug discontinuation or require therapy.

All AEs with a date of onset up to 30 days following after the patient has stopped study participation (defined as time of last dose of study drug taken or last visit whichever is later) must be reported.

The occurrence of AEs should be sought by non-directive questioning of the patient at each visit during the study. AEs may also be detected when they are volunteered by the patient during or between visits or through physical examination, laboratory test, or other assessments. All adverse events must be recorded on the Adverse Events CRF with the following information:

- 1. the severity grade (mild, moderate, severe)
- 2. its relationship to the study drug(s) (suspected/not suspected)
- 3. its duration (start and end dates or if continuing at final exam)
- 4. whether it constitutes a serious adverse event (SAE)

All AEs should be treated appropriately. Treatment may include 1 or more of the following: no action taken (i.e. further observation only); study drug dosage adjusted/temporarily interrupted; study drug permanently discontinued due to this adverse event; concomitant medication given; non-drug therapy given; patient hospitalized/patient's hospitalization prolonged. The action taken to treat the AE should be recorded on the Adverse Event CRF.

Once an adverse event is detected, it should be followed until its resolution or until it is judged to be permanent, and assessment should be made at each visit (or more frequently, if necessary) of any changes in severity, seriousness, the suspected relationship to the study drug, the interventions required to treat it, and the outcome.

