9.5.3 Safety variables

Adverse events

Treatment emergent adverse events (events started after the first dose of study treatment or events present prior to the first dose of study treatment but increased in severity based on preferred term) will be summarized.

AEs will be summarized by presenting, for each treatment group, the number and percentage of subjects having any AE, having an AE in each primary system organ class and having each individual AE (preferred term). Summaries will also be presented for AEs by severity and for study treatment related AEs. If a subject reported more than one adverse event with the same preferred term, the adverse event with the greatest severity will be presented. If a subject reported more than one adverse event within the same primary system organ class, the subject will be counted only once with the greatest severity at the system organ class level, where applicable. Serious adverse events will also be summarized.

These summaries will be presented separately by study periods, i.e. Weeks 1-16 and after Week

As appropriate, the incidence of AEs will be presented per 100 subject years of exposure.

Separate summaries will be provided for death, serious adverse event, other significant adverse events leading to discontinuation and adverse events leading to dose adjustment (including study treatment discontinuation).

A graphical display of relative frequencies within system organ classes and relative risks, as appropriate, will be presented.

When adjudication is required of major cardiovascular events, a summary of those types of events as reported by the investigator and confirmed by adjudication will be provided.

Laboratory data

The summary of laboratory evaluations will be presented for three groups of laboratory tests (hematology, serum chemistry and urinalysis). Descriptive summary statistics for the change from baseline to each study visit will be presented. These descriptive summaries will be presented by test group, laboratory test and treatment group. Change from baseline will only be summarized for subjects with both baseline and post baseline.

For each parameter, the maximum change from baseline within each study period will be evaluated analogously.

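### SAP 2.8.1 ends treatment-emergent events 30 days after the last dose, an undeclared change that leaves late non-serious events collected under the protocol outside the general AE summaries

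*SAP*

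**What the plan says.** **Protocol 9.5.3 (Safety variables)** defines treatment-emergent events as "events started after the first dose of study treatment or events present prior to the first dose of study treatment but increased in severity". It gives no end date.

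**Protocol 7.1 (Adverse events)** requires reporting of "All AEs with a date of onset up to 30 days following after the patient has stopped study participation". The end of participation is "defined as time of last dose of study drug taken or last visit whichever is later". Protocol 7.2.2 uses the same end point for SAEs.

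**SAP 2.8.1 (Adverse events)** takes over the starting rule from 9.5.3 and attaches "events until 30 days for AE and SAE after last dose of study treatment". It promises a listing of non-treatment-emergent events, but describes them this way: "These adverse events occurred before the first dose of the study treatment".

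**SAP 2.8 (Safety analyses)** confines follow-up analyses to summaries of treatment-emergent events and SAEs. **SAP section 4**, where departures from the protocol's analyses would be declared, is marked not applicable.

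**Visit timing.** Protocol 3.1 places a follow-up visit 4 weeks after the last administration for every subject, early leavers included. Protocol 5.5.9 gives leavers an end-of-treatment visit and also a Week 24 visit, which it equates with 4 weeks after last treatment. Protocol section 6 puts the leavers' end-of-treatment visit at 4 weeks after the last administration, with the Week 24 follow-up in addition. Section 6 also sets minimum safety contact over the 30 days after the Week 20 visit, "including a final contact at the 30-day point".

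**The concern.** The SAP narrows the protocol's definition of the events that fill the main safety tables and does not say so. Sites must report events after the SAP window has closed. Under the SAP's stated rules those events are not treatment-emergent, and they are not pre-dose events either. A late non-serious event therefore has no named summary and no dedicated listing.

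At stake is whether the safety report is complete against the protocol. No efficacy result is involved. The point matters most for patients who stop early, because on some readings of the visit schedule their collection period runs well past the SAP window.

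**Working it through.** The plan states no figure for this gap, so there is none to reproduce. The check is date arithmetic and assumes that visits and injections take place on schedule.

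**Inputs**
- Scheduled day = 7 × week + 1. This gives Week 20 = 7 × 20 + 1 = Day 141, which agrees with SAP Table 2-1, and Week 24 = Day 169.
- SAP window closes at last dose + 30 days (SAP 2.8.1).
- Collection ends at max(last dose, last visit) + 30 days (Protocol 7.1).
- Follow-up visit 4 weeks (28 days) after last dose (Protocol 3.1).

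**Completer, last dose at Week 20**
- SAP window closes: 141 + 30 = Day 171.
- Last visit: 141 + 28 = Day 169. Collection ends: 169 + 30 = Day 199.
- Gap: 199 − 171 = 28 days (onset on Days 172 to 199).
- Post-dose collection: 199 − 141 = 58 days. The gap is 28/58 = 48% of those days. This is a share of days, not of events.
- Minimum final contact under Protocol section 6: 141 + 30 = Day 171, the same day the SAP window closes.

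**Early leaver, last dose on Day L**
- Reading A, last visit 4 weeks after last dose: collection ends at L + 28 + 30 = L + 58. Gap = 58 − 30 = 28 days.
- Reading B, end-of-treatment visit 4 weeks after last dose and follow-up 4 weeks after that: collection ends at L + 56 + 30 = L + 86. Gap = 86 − 30 = 56 days.
- Reading C, follow-up at calendar Week 24: collection ends on Day 199. Gap = 199 − (L + 30) = 169 − L.

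| Last dose | L | SAP window closes | Gap A | Gap B | Gap C |
|---|---|---|---|---|---|
| Week 16 | 113 | 143 | 28 | 56 | 56 |
| Week 12 | 85 | 115 | 28 | 56 | 84 |
| Week 8 | 57 | 87 | 28 | 56 | 112 |
| Week 4 | 29 | 59 | 28 | 56 | 140 |

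**Where an event in the gap can be reported**
- Treatment-emergent summaries: no, because of the limit in SAP 2.8.1.
- Non-treatment-emergent listing: no, as described, because it holds pre-dose events.
- Follow-up summaries: only if serious (SAP 2.8).
- SAE, special-interest and death sections (SAP 2.8.1.1, 2.8.1.2, 2.8.2): possibly, since none repeats the limit.
- General listings: possibly. SAP 2.1.2 says that everything collected will be listed, although the sentence stands in the section on visit windows.

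**The case against.** The strongest reply is that a 30-day post-dose window is a reasonable analysis choice and that little is lost. Several parts of that reply stand.

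- **The window is not wrong in itself.** A reader might infer from the protocol's longer post-dose precautions, such as "Live vaccines should not be given until 12 weeks after last study treatment administration", that 30 days is too short. Those are precautions, not analysis windows. The 12-week interval (84 days) also exceeds the 58 days over which a completer's events are collected, so it cannot justify that period either.
- **Late events need not vanish.** A reader might infer that they have no output at all, or that SAEs, deaths and infections or bowel inflammation of special interest are certainly under-counted. The documents do not support this. A general listing may show them, and the sections on SAEs, special interest and deaths carry no limit of their own. The SAP leaves the matter open.
- **The large gaps rest on one reading.** A reader might take 112 days as the size of the problem for early leavers. It applies to a Week 8 last dose with a return at calendar Week 24. Other passages give 28 or 56 days.
- **The section 6 contact does not contradict 7.1.** It is expressed as a minimum. However, no contact is scheduled for a completer after Day 171, so events in the gap would come mainly from spontaneous reports and may be few.
- **Simply removing the limit has a cost.** SAP 2.4.1 ends exposure with the treatment period, so counting events to Day 199 in exposure-adjusted rates would inflate them. Protocol 5.5.13 also allows other treatment after withdrawal.

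It could also be argued that the added phrase sets no limit. But the starting rule alone already admits every later event, so the phrase has an effect only if it closes the window. If no limit was meant, the text still needs correcting.

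None of this explains why the change is undeclared or why late non-serious events have no named summary.

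**Conclusion.** The point holds as a mismatch between protocol and SAP in safety reporting. The SAP shortens the treatment-emergent period without declaring it. Late non-serious events that the protocol requires to be reported then fall outside the general AE summaries and outside the non-treatment-emergent listing.

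The size is 28 days for a completer. For early leavers it depends on how conflicting visit passages are read, as tabulated above. These figures assume on-schedule visits and that the added SAP phrase is a limit. The number of events affected cannot be derived from the documents, so no claim about bias in incidence is justified. The conclusion is that reporting is incomplete against the protocol and that the reporting period for SAEs, deaths and events of special interest is unstated.

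**What to change.** In the SAP, before database lock, choose one of two routes:

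1. Restore the Protocol 9.5.3 definition up to the end of the 7.1 collection period, and flag events with onset more than 30 days after the last dose.
2. Keep the 30-day window, declare it in section 4, and add a separate crude-incidence summary and a listing of events with onset after it, including those of special interest.

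Under either route:
- State that SAEs and deaths are summarised to the end of collection.
- Restrict exposure-adjusted rates to events within the matching exposure period.
- Reword the description of the non-treatment-emergent listing so that late events have a stated place.

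Protocol 3.1, 5.5.9, section 6 and 7.1 must be reconciled on when leavers have their end-of-treatment and follow-up visits and when AE collection ends. This review does not say which timing is right. A protocol change may reach few patients, since about 190 had been recruited when Amendment 1 was written, but the SAP still needs the answer to fix the end of each leaver's window.

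The cost is SAP wording, a changed or added flag, and one extra table and listing. The downside is a slightly higher reported crude incidence that includes events remote from the last dose.
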